### **(ii) Subjects to be included**

**Study subjects:** In the Part I randomized controlled trial (RCT), 294 eligible workers from 3 non-healthcare work settings will be recruited, and randomized into intervention group (147 subjects) and control group (147 subjects). To be eligible to the Part I RCT, all participants are required to be aged 18 or above, who can read Chinese and currently being employed in three non-healthcare work settings from non-office, mobile, and office work environment in Hong Kong. We attempt to follow-up all participants of the RCT for 9 months to observe the effectiveness of the intervention on improving the primary outcomes, i.e., attitude to vaccination and SARS-CoV-2 testing.

In Part II longitudinal quantitative study, we plan to recruit a total of 1,495 workers who are aged 18 or above and currently working in non-office, mobile, or office work setting in Hong Kong. All eligible study subjects in Part II longitudinal/ prospective cohort study will be recruited in the timeline of 1.5th -3.5th year of the project and followed up for 2 years to observe the changes of attitude to vaccination and virus testing as well as risk profiles of workers towards outbreaks over time.

Figure 1. Workflow chart of hazard identification of outbreaks and control measures in work settings

\* After considering a lost-to-follow-up rate of about 40%

In the Part III longitudinal qualitative study, we plan to recruit an overall 26 management staff and frontline workers (in a ratio of 1:2) with same inclusion/exclusion criteria as the Part I & II study, i.e., aged 18 or above and currently being employed in three non-healthcare work settings from non-office, mobile, and office work environment in Hong Kong.

All above planned number of participants to be enrolled in the baseline of the Part I, II and III study have already considered a potential loss-to-follow-up rate of about 40%.

**Settings:** The 3 work settings are categorized by types as below according to their job nature and working environment:

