**Sample size:** We estimated sample size for the Part I – Randomized controlled trial according to two independent proportions power analysis. As there is no relevant data of willingness to vaccination on our target subjects to guide the sample size calculation regarding an educational intervention against COVID-19, we employed a conservative assumption that the intervention will make a 20% change for worker's attitude to vaccination/virus test, sample size for both groups/arms will be 124, 130, 124, 109 and 79 for the proportion of willingness to vaccination/virus test of 30%, 40%, 50%, 60%, and 70%, respectively, with a 90% G-power. Therefore, a minimal 79 pairs subjects are required to achieve the primary objective (RCT) of this proposal project; if further assuming a loss-to-follow-up rate of about 40%, then an overall 222 participants with 111 subjects in the intervention group and 111 subjects in the control group are required. However, if given the most conservative sample size estimation with 40% loss-to-

follow-up rate, a total of 364 subjects with 182 subjects in each arm of RCT ( $130*1.4$ ) are required. Therefore, the overall sample size for RCT could reasonably range from 222 to 364 to satisfy the primary research objective of this proposal project. In the proposed RCT, we considered taking the mean of the “most-least conservative” sample sizes of 294 [ $(222+364)/2$ ] from G-power as a reasonable sample size with 147 subjects in each arm, and this sample size (i.e., 294) has already taken into consideration a potential loss-to-follow-up rate of about 40%.

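### The RCT total of 294 does not preserve the 90% power it is built from: at the plan's own 40% loss, four of its five scenarios fall to 76–83%

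*Combined protocol and SAP*

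**What the plan says.** Under (ii) Subjects to be included, Sample size, the RCT is sized "according to two independent proportions power analysis". The working assumption is that "the intervention will make a 20% change for worker's attitude to vaccination/virus test". The numbers required "with a 90% G-power" are given as "124, 130, 124, 109 and 79 for the proportion of willingness to vaccination/virus test of 30%, 40%, 50%, 60%, and 70%, respectively".

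The plan then takes the two extremes:

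- The smallest, 79 per arm, becomes 111 per arm (222 in total) after the allowance for 40% loss.
- The largest, 130 per arm, becomes "a total of 364 subjects with 182 subjects in each arm of RCT", with the working printed as 130*1.4.

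The final size is the mean of 222 and 364, taken as 294, or 147 per arm. The section closes by saying that "this sample size (i.e., 294) has already taken into consideration a potential loss-to-follow-up rate of about 40" per cent. The Study subjects paragraph gives the same assurance for Parts I to III: the planned baseline numbers "have already considered a potential loss-to-follow-up rate of about 40" per cent.

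**The concern.** Two separate steps look wrong.

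**Loss allowance.** To have n participants left after a proportion L is lost, n/(1 − L) must be randomised. Multiplying by 1 + L always gives too few, and the gap is large when L is 40%.

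**Averaging.** The plan says it has no data on starting willingness in these workers. A size halfway between the most and least favourable scenarios carries no power guarantee of its own; it is too small for any scenario that needs more than the midpoint. Part II meets the same uncertainty by setting the proportion at 0.5 to obtain the maximum size. Part I gives no reason for doing otherwise.

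What is at stake is how the primary result will be read. A reader who takes 294 as a 90%-power design would put the chance of missing a true 20-point effect at 10%. If it is really 17% to 24% in most of the scenarios considered, a null result is weaker evidence than it appears.

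**Working it through.** **Inputs from the plan.** Two independent proportions; 20% change; 90% power; starting proportions 30% to 70%; 1:1 allocation with 147 per arm; 40% loss (all from section ii); significance at p < 0.05 (section iv). Two readings are inferred because they reproduce the plan's figures. The change is absolute (p to p + 0.20): a relative 20% change would need 188 to 1,289 per arm. The test is two-sided: a one-sided test gives 101, 106, 101, 89 and 67.

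**Step 1: reproduce the plan's per-arm sizes.** The pooled formula is

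n = [1.960·√(2p̄(1−p̄)) + 1.282·√(p₁(1−p₁) + p₂(1−p₂))]² / 0.20², with p̄ the mean of p₁ and p₂.

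For 40% vs 60%: p̄ = 0.5, so n = [1.960 × 0.7071 + 1.282 × 0.6928]² / 0.04 = 129.3, rounded up to 130. The five scenarios give 124, 130, 124, 109 and 82. Four match exactly. The plan's 79 for the last is what the unpooled and arcsine formulas give.

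**Step 2: reproduce the final size.** 79 × 1.4 = 110.6, rounded to 111 (222 in total). 130 × 1.4 = 182 (364 in total). (222 + 364)/2 = 293, taken as 294 for equal arms. That rounding is immaterial.

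**Step 3: check the loss allowance.** The factor 1.4 preserves n only up to a loss of 1 − 1/1.4 = 28.6%. At 40% loss the plan's two inflated sizes leave 182 × 0.6 = 109 (needed: 130) and 111 × 0.6 = 67 (needed: 79), so both ends of its range miss their own targets. Dividing by 0.6 gives 207, 217, 207, 182 and 132 per arm. The range then runs from 2 × 132 = 264 to 2 × 217 = 434.

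**Step 4: evaluable numbers at 294.** With 40% loss, 147 × 0.6 = 88.2, about 88 per arm. If the 1.4 factor is accepted, 147/1.4 = 105 per arm, which isolates the effect of averaging. Both are below four of the five stated requirements, before any power is computed.

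**Step 5: power.** Power = Φ{[0.20·√n − 1.960·√(2p̄(1−p̄))] / √(p₁(1−p₁) + p₂(1−p₂))}. For 40% vs 60% at n = 88: (1.876 − 1.386)/0.693 = 0.708, and Φ(0.708) = 76.0%.

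| Scenario | Plan's n per arm | Power at 88 | Power at 105 | Power at 147 (no loss) | Largest loss leaving plan's n (1 − n/147) | Difference detectable at 90% power, 88 per arm |
|---|---|---|---|---|---|---|
| 30% vs 50% | 124 | 77.8% | 84.6% | 94.2% | 15.6% | 23.8 points |
| 40% vs 60% | 130 | 76.0% | 83.1% | 93.3% | 11.6% | 24.1 points |
| 50% vs 70% | 124 | 77.8% | 84.6% | 94.2% | 15.6% | 23.5 points |
| 60% vs 80% | 109 | 83.1% | 89.1% | 96.6% | 25.9% | 21.9 points |
| 70% vs 90% | 79 | 91.9% | 95.7% | 99.2% | 46.3% | 19.4 points |

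Exact power of the chi-square test at 88 per arm is 78.9%, 77.3%, 78.9%, 83.8% and 92.7%. The unpooled and arcsine approximations also leave the first four scenarios below 90%.

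**The case against.** **The plan never states a power for 294.** The 90% is attached to the five scenario sizes, and 294 is only called reasonable. This is correct as a reading. But 90% is the only power given, 294 is built solely from sizes computed at that power, and the plan says the loss is already covered. The implication is clear even though it is not spelled out.

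**Averaging is a disclosed compromise, not an arithmetic slip.** Also fair: only the 1.4 factor is an arithmetic error. Taken alone, averaging leaves 83% to 96% power, and the 60% scenario is borderline (89.1% pooled, 90.0% unpooled). The firm count of four in five comes from both steps together.

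**Lost participants may still contribute.** Outcomes are measured at months 3, 6 and 9, and section (iv) mentions linear and Cox models, attitude scores and intention-to-treat analysis. Some information could be recovered, and a continuous analysis would have different power. However, the plan does not use any of this to justify 294, and intention-to-treat analysis does not by itself replace missing outcomes. The powers above describe the plan's own sizing model.

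**Loss may be lower than 40%.** With no loss, 147 per arm gives at least 93% power throughout. But 40% is the plan's own figure, and the size is presented as covering it.

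**The correction is only wording, and the plan gives no rule for reading a null result.** Both are true. Low cost does not make the stated justification correct.

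**Conclusion.** The concern holds. At the plan's assumed 40% loss, 294 randomised leaves about 88 evaluable per arm, and power for a 20-point difference is 76% to 83% at starting willingness of 30% to 60%. Only the 70% scenario, at 92%, reaches 90%. The shortfall is about 7 to 14 percentage points.

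This rests on the plan's loss rate and two-proportion model, on the inferred two-sided 5% test and absolute 20-point change, and on lost participants contributing no outcome. The four-in-five count does not depend on which formula is used. Because the plan says it does not know the starting proportion, it cannot rely on the one favourable scenario. This should be corrected before the design is relied on: it is the only sizing argument for the randomised comparison.

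**What to change.** Keep 294 if that is what is feasible, remove the averaging as a rationale, and state the actual property. For example: *With 294 randomised and 40% loss (about 88 evaluable per arm), power for a 20-point difference is 76–83% for a starting willingness of 30–60% and 92% for 70% (two-sided 5%); the difference detectable with 90% power is about 19–24 points.* State the two-sided test and the absolute difference explicitly.

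Replace the 1.4 factor with division by 0.6. If a range is printed, it becomes 264 to 434. Full 90% cover of the 40% vs 60% scenario at 40% loss would take 434, but this correction does not require enrolling more.

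Amend the loss-to-follow-up assurance in the Study subjects paragraph to match. The same factor is used for Part II (1,068 × 1.4 = 1,495) and Part III (18 × 1.4 = 25.2, taken as 26), so those statements need the same check.

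The cost is protocol wording and a less favourable stated power; no extra participants are needed.

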We estimated sample size for the Part II – Longitudinal/prospective cohort study (quantitative survey) according to the formula for cohort studies. As there is no relevant publication for a reference, a conservative estimation is used to calculate the sample size for Part II study. For the estimation of the maximum sample size of longitudinally quantitative survey for the Part II study, the presumed population proportion is set as 0.5, which means that half of the workers have positive attitude to vaccination or willingness of SARS-Cov-2 virus testing in the selected work settings. It is estimated that a minimum of 1,068 workers is required for the longitudinal/prospective cohort study to accept an absolute sample error of 3.0% at 95% confidence level. Currently, there is not enough guideline for choosing an appropriate absolute error, and an absolute error of 5% is generally recommended in many studies. So, an absolute error of 3.0% employed in the project is more conservative than many other studies for sample size estimation. Although the required sample size is getting larger with the increase of population size, it will not change much when the population size is larger than 20,000. According to the latest statistics of the Census and Statistics Department of Hong Kong, the employed persons during 12/2020 - 2/2021 in Hong Kong are about 3.6 million, and therefore, it is appropriate to adopt this method of sample size calculation for a population-based cohort study in Hong Kong working settings. Assuming a potential loss-to-follow-up rate of about 40%, 1,495 workers are suggested to be recruited in the baseline survey for the Part II study.

While there is no established requirement for sample size estimation for the Part III and IV study which only involve qualitative approach and workplace hygiene measurement, it usually desires a reasonable sample size with representative sample. We plan to recruit 26 ( $18*1.4$ ) eligible subjects at the baseline from 3 defined work settings to participate in the Part III qualitative study and 6 representative workplaces for the Part IV study that are regarded as reasonable. We set the sample size according to number of participants/workplaces estimated to reach data saturation.

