### *(iii.2) Procedure of Part II study*

**Part II** study includes longitudinal quantitative study (i.e., prospective cohort study) from the timeline of 1.5th – 4.5th year involving an overall 1,495 workers recruited at the baseline survey from non-office, mobile and office work settings. At the baseline survey, 1,495 workers from 3 studied work settings will be invited to respond to a standardized questionnaire on exposure,

prevention and attitude towards outbreaks, and willingness to be tested for COVID-19 and receiving vaccination. Results obtained from the baseline and follow-up surveys will be compared to understand the changes of attitudes, awareness, willingness to vaccination and virus test, and workplace risk profile of workers towards prevention and control of COVID-19.

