### **Cohort enumeration at baseline and follow-up:**

A two-stage sampling method will be employed to recruit 1,495 eligible cohort members at the baseline survey for the Part II longitudinal quantitative study (i.e., prospective cohort study) in the timeline of 1.5th-2.5th year. In stage one, we plan to invite local workers unions with non-office, mobile and office work settings through our networks and connections, such as the Federation of Hong Kong and Kowloon Labour Unions (FLU). There are more than 150 local worker unions under the network of FLU, covering a variety of types of worker unions including restaurants, transportation, construction, telephone and communication, etc. In stage two, we will then recruit about 1,495 workers from the worker unions who agree to participate in the Part II study of our project. However, the baseline recruitment of Part II study subjects will be stopped if the required sample size of workers is reached.

All eligible subjects recruited at the baseline will be invited to participate in the follow-up survey in the timeline of 3.5th- 4.5th year to compare the changes of attitude to vaccination and virus testing as well as risk profile toward infection control in the workplace through various means (e.g., telephone, email, worker unions). Any loss-to-follow-up will be recorded.

Participants who complete the whole questionnaire of the baseline or follow-up quantitative survey will receive 200HKD fast food restaurant / supermarket coupon, and if the participant completes both the baseline and follow-up quantitative questionnaire survey, she/he will receive a total of \$400 fast food restaurant / supermarket coupon as a token of appreciation.

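### Part II's 1,495 does not absorb its stated 40% loss (897 remain against a minimum of 1,068), and recruitment through unions is ignored in both sample size and analysis

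*Combined protocol and SAP*

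**What the plan says.** Section (ii), Sample size, assumes a proportion of 0.5 for Part II and states: "It is estimated that a minimum of 1,068 workers is required for the longitudinal/prospective cohort study to accept an absolute sample error of 3.0" per cent, at 95% confidence. It continues: "Assuming a potential loss-to-follow-up rate of about 40%, 1,495 workers are suggested to be recruited in the baseline survey". Earlier in section (ii), the planned numbers "in the baseline of the Part I, II and III study have already considered a potential loss-to-follow-up rate of about 40" per cent.

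Section (iii.2) gives the purpose of the second survey: "Results obtained from the baseline and follow-up surveys will be compared to understand the changes of attitudes", among other outcomes.

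Under Cohort enumeration at baseline and follow-up, recruitment is in two stages: "A two-stage sampling method will be employed to recruit 1,495 eligible cohort members at the baseline survey". In stage one, "we plan to invite local workers unions with non-office, mobile and office work settings through our networks and connections". One federation is named as an example: "There are more than 150 local worker unions under the network of FLU". In stage two the team will "recruit about 1,495 workers from the worker unions who agree to participate". The number of unions to be recruited is not given.

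Section (iv) lists chi-square tests, paired t-tests, covariance analysis, structural equation models and regression models. It mentions no union effect, cluster-robust variance, survey-design adjustment or weighting.

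**The concern.** There are two separate faults.

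**Loss to follow-up.** If 40% of 1,495 workers are lost, fewer than 1,068 remain, so the plan misses its own minimum under its own assumption. The shortfall falls on the follow-up survey, which is half of the baseline-to-follow-up comparison that Part II exists to make.

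**Clustering.** Workers in one union share an occupation and often a workplace culture, so their attitudes may be correlated. If they are, a simple-random-sample formula overstates precision, and tests that treat workers as independent understate standard errors. The effect is greatest for single proportions and for comparisons that run between unions. Work setting is one of these: the unions described are largely occupational (restaurants, transportation, construction), and section (iv) names work setting as a comparison for the baseline chi-square tests. The effect is smaller for change within a worker and for predictors that vary within unions. The clustering point concerns Part II only and does not bear on the RCT.

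**Working it through.** **Inputs from section (ii).** p = 0.5; absolute error 0.03; 95% confidence (z = 1.96); loss 40%; baseline N = 1,495; employed population about 3.6 million.

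**1. Reproduce the plan's minimum.** n = z²p(1 − p)/e² = 1.96² × 0.25/0.03² = 1,067.1, rounded up to 1,068. The stated figure is correct. A finite-population correction for 3.6 million gives 1,066.8, so it makes no difference.

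**2. Reproduce 1,495.** 1,068 × 1.4 = 1,495.2, which matches. Dividing by the retained fraction gives 1,068/0.6 = 1,780, which does not. The factor 1.4 is inferred for Part II; the plan writes it out only for Part I (130 × 1.4) and Part III (18 × 1.4). The shortfall below does not depend on that inference.

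**3. Apply the stated loss.** 1,495 × 0.6 = 897, and 1,068 − 897 = 171 short.

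**4. Margins under the plan's own formula, z√(p(1 − p)/n).**

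| Survey | n | Margin at p = 0.5 |
|---|---|---|
| Baseline | 1,495 | 2.53 points |
| Follow-up after 40% loss | 897 | 3.27 points |

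**5. When 3.0 points would still hold at follow-up.** Either loss is at most 1 − 1,068/1,495 = 28.6%, or p is about 0.30 or lower, or 0.70 or higher.

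**6. Clustering, single proportions.** The documents give no intraclass correlation (ICC) and no number of unions, so these inputs are assumptions: ICC 0.01 to 0.05, and 10 to 50 baseline workers per union. Ten is about 1,495/150 = 9.97, if 150 unions all take part; 50 implies about 30 unions. With 40% loss spread evenly, the cluster sizes fall to 6 and 30. Design effect = 1 + (m − 1) × ICC, and the margin is multiplied by its square root.

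| Survey | m | ICC | Design effect | Margin |
|---|---|---|---|---|
| Baseline | 10 | 0.01 | 1.09 | 2.65 |
| Baseline | 50 | 0.05 | 3.45 | 4.71 |
| Follow-up | 6 | 0.01 | 1.05 | 3.35 |
| Follow-up | 30 | 0.05 | 2.45 | 5.12 |

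If whole unions dropped out, so that cluster sizes stayed at 10 and 50, the follow-up range would be 3.42 to 6.08. The baseline margin stays within 3.0 up to a design effect of 1,495/1,067.1 = 1.40.

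**7. Clustering, within-worker change.** Let ru be the between-wave correlation of union effects and rw that of worker residuals. Then ICC for change = ICC(1 − ru)/[ICC(1 − ru) + (1 − ICC)(1 − rw)]. With assumed ru = 0.8 and rw = 0.5:

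- ICC 0.01 gives 0.0040, so the design effect at m = 6 is 1 + 5 × 0.0040 = 1.02.
- ICC 0.05 gives 0.0206, so the design effect at m = 30 is 1 + 29 × 0.0206 = 1.60.
- If union effects are fully stable (ru = 1), the design effect is 1.0.

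**The case against.** The loss of precision in the first part is small. The plan itself notes that a 5% error is commonly recommended and chose 3.0% as stricter; 3.27 is well inside 5. The proportion of 0.5 is a worst case, the loss is only approximate, and the baseline survey is unharmed. All of this is true and limits the importance of the point. It does not rescue the statement: loss would have to be 28.6% or less, which is not about 40%, and if 1,068 were needed only at baseline there would have been no reason to inflate for loss.

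On clustering, every magnitude is assumed, and the upper figures combine the least favourable values. More than 150 unions are available in one network, so there could be fewer than 10 workers per union, and for within-worker change the effect may be nil. Section (iv) is also a short list of methods, so silence on union is not proof that it would be ignored in every model. These limits stand. But a plain chi-square or paired t-test does assume independence between workers (the paired test deals only with repeated measures on the same worker), and nothing in section (iv) tells the analyst to do otherwise.

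Finally, a design effect corrects variance only. Unions approached through networks and free to decline are not a probability sample. That is a real further limitation, and the fix includes it.

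**Conclusion.** Both parts hold. The first is certain from the documents' own figures: 897 remain after the stated loss, not 1,068, and the follow-up margin at p = 0.5 is 3.27 points rather than 3.0, a modest shortfall of 0.27 points. The statement that the Part II number already covers 40% loss is therefore wrong as written.

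The second is an omission whose direction is clear if answers correlate within unions, but whose size the documents do not fix. The ranges in the working are illustrative and rest on the assumed ICC, cluster sizes and between-wave correlations. Taken together, the faults should be corrected. They do not undermine the Part II design.

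**What to change.** - In section (ii), keep 1,495 and restate the expected follow-up margin as about 3.3 points at p = 0.5 with 897 retained, before any design effect. Note that holding 3.0 points after 40% loss would need 1,068/0.6 = 1,780 at baseline, which is 285 more.
- Record the union of every Part II participant at recruitment, when it is known.
- In section (iv), specify union as the cluster for Part II: survey procedures, generalised estimating equations (with a small-sample correction if unions are few), or a random union effect. For change, apply the same clustering to within-worker differences.
- State that the margin describes sampling error only and excludes selection error, because unions are invited through networks and may decline.

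The cost is wording in the protocol and SAP plus one identifier in the data. No extra participants are needed. The price is somewhat wider intervals and a slightly less favourable stated margin.

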### **Questionnaire development:**

A standardized questionnaire is designed to capture each participant's information on knowledge, attitude and awareness towards SARS-CoV-2, exposure prevention behaviour, and willingness to vaccination and virus testing, with key items on –

- General introduction
- Employment status, industry background and occupation, job nature and tasks, demographics
- Worker's exposure and prevention profile towards risks of outbreaks, including knowledge of engineering and administrative control measures (e.g., proper utility of personal protective equipment, social distancing), safety culture, types of occupational hazards/hazardous process
- Attitude and willingness to vaccination and SARS-CoV-2 testing, and barriers
- Previous work and related exposure behaviour and behaviour intention towards prevention of infectious diseases in the workplace

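### Part II's 3.0% margin is justified as if for a population-based cohort, but recruitment through agreeing unions is a non-probability sample, so the margin excludes selection error

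*Combined protocol and SAP*

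**What the plan says.** The Part II sample size paragraph, in (ii) Subjects to be included, works from a single proportion: "the presumed population proportion is set as 0.5, which means that half of the workers have positive attitude to vaccination" or are willing to be tested, in the selected work settings. From this it derives that "a minimum of 1,068 workers is required for the longitudinal/prospective cohort study to accept an absolute sample error of 3.0% at 95% confidence level". It then remarks that the required number hardly changes once the population exceeds 20,000, notes that "the employed persons during 12/2020 - 2/2021 in Hong Kong are about 3.6 million", and concludes that "it is appropriate to adopt this method of sample size calculation for a population-based cohort study in Hong Kong working settings". The baseline target follows: "Assuming a potential loss-to-follow-up rate of about 40%, 1,495 workers are suggested to be recruited in the baseline survey".

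Recruitment is described in (iii.2), under Cohort enumeration at baseline and follow-up. The method is called two-stage sampling. In stage one, "we plan to invite local workers unions with non-office, mobile and office work settings through our networks and connections"; a federation with more than 150 unions is given as an example. In stage two, "we will then recruit about 1,495 workers from the worker unions who agree to participate". Recruitment stops when the required number is reached.

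Eligibility in (ii) asks for age 18 or above and current work in one of the three settings. Union membership is not required. Section (iv) Data processing & analysis plans descriptive statistics, Chi-square tests, paired t-tests, covariance analysis, regression and structural equation models. It mentions no weighting and no limit on generalisation.

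**The concern.** A margin of 3.0 points at 95% confidence has its usual meaning only if the sample is drawn from the stated population with known selection probabilities. The sample size paragraph presents the study as having that property. The recruitment paragraph gives no step that would provide it: no list of unions or workers to draw from, no random draw at either stage, and no quota by setting or industry. Non-union workers are eligible, but no route to them is described.

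What is at stake is the reading of any pooled proportion from Part II, such as the share of workers with a positive attitude to vaccination. That figure will depend on which unions agree and which members respond. The plan itself describes the three settings as differing in contact with the public and in COVID-19 risk, and intends to compare willingness between them, so the mix of settings may matter. A reader who sees a population-based label and a 3.0% error would take the figure as an estimate for Hong Kong workers in these settings, with an uncertainty that leaves out selection. The project is also meant to inform policy.

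**Working it through.** **Inputs from the Part II sample size paragraph:** p = 0.5; absolute error d = 0.03; 95% confidence (z = 1.96); population about 3.6 million; loss to follow-up about 40%.

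**Reproducing the plan's figures**

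- n = z² × p(1 − p) / d² = 1.96² × 0.25 / 0.03² = 1,067.1, rounded up to 1,068. This matches.
- With a finite-population correction, n / (1 + (n − 1)/N) gives 1,066.8 at N = 3.6 million and about 1,013 at N = 20,000. The remark that population size matters little beyond 20,000 is sound.
- 1,068 × 1.4 = 1,495.2, which matches 1,495.

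The arithmetic is not in dispute.

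**Setting the formula against the recruitment**

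- Population: the formula assumes a sample of workers in the selected settings in Hong Kong. Recruitment reaches workers in unions known to the team that agree to take part.
- Selection: the formula assumes simple random sampling. The two-stage method named in (iii.2) has no stated frame, random draw or selection probabilities.
- Composition: the mix of settings and industries is not controlled by quotas, and (iv) names no weights to adjust it afterwards.

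The 3.0% is therefore the sampling error of a hypothetical simple random sample of 1,068. It contains nothing for selection.

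**Illustration of what an omitted bias does**

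The documents give no bias, so these values are assumptions. With SE = √(0.25/1,068) = 0.0153 and bias b, coverage = Φ(1.96 − b/SE) − Φ(−1.96 − b/SE).

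- b = 1 point: b/SE = 0.65, coverage about 90%.
- b = 2 points: b/SE = 1.31, coverage about 74%.
- b = 3 points: b/SE = 1.96, coverage about 50%.

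A larger sample does not help. At the baseline target of 1,495 the same biases give about 88%, 66% and 36%, because the interval narrows around the same displaced value.

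**The case against.** The strongest reply is that the single-proportion formula is only a sizing device. The presumed proportion is for workers in the selected settings, and the 3.6 million figure appears only to show that the finite-population correction can be ignored. Part II is described as a study of change over time, and (iv) plans group comparisons, paired changes and association models. It names no pooled workforce prevalence. The unions are sought deliberately across all three settings. The sample size section ties the primary objective to the randomized trial, which this point does not touch.

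Most of that stands, and it limits the point. Four stronger readings are tempting but are not supported by the documents:

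- That Part II claims to represent all 3.6 million employed persons. The target is workers in three non-healthcare settings.
- That a pooled figure will be published as a workforce estimate. The plan does not say so; the label and the margin merely invite that reading.
- That the bias exceeds the 3.0 points. Nothing in the documents gives its size or direction, and a small bias would do little harm.
- That Part II as a whole is invalid. Within-cohort change and associations depend less on representativeness, although generalising them is still limited.

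The absence of random selection within unions and of weighting is inferred from silence. The reply does not, however, supply a basis for calling the cohort population-based or for reading 3.0% as a margin for Hong Kong workers. Inviting unions from all three settings is not a probability sample of any of them.

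**Conclusion.** The point holds as a mismatch between the stated design and the described recruitment. The number 1,068 is computed correctly, but its 3.0% is nominal simple-random-sampling error, and pooled Part II proportions do not estimate the proportion among Hong Kong workers in the three settings with that accuracy. The coverage figures show how sensitive the interval is to biases of a few points; they do not estimate the actual bias. The conclusion rests on (iii.2) being the full account of recruitment. If a frame and random selection at both stages exist but were left out of the text, adding them would answer much of the point. This is worth correcting before results are reported, but it does not threaten the trial's primary objective.

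**What to change.** **In (ii), Part II sample size:** delete the population-based label. State that the 3.0% is nominal sampling error under simple random sampling, that it excludes selection, and that it is not a margin for the Hong Kong workforce. Tying the 3.0% to members of the participating unions would not be enough, since no random selection within unions is stated either.

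**In (iv):** report Part II proportions by work setting as well as pooled, and limit conclusions to the recruited union-based sample.

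**Optional sensitivity analysis, shown beside the unweighted figures:** post-stratify to official employed-persons margins restricted to the study's non-healthcare occupations, where matching margins exist and the variables are collected. The questionnaire covers "Employment status, industry background and occupation, job nature and tasks, demographics", which may suffice, but it does not name age or sex. The plan cites only a workforce total from the official source, so the availability of matching margins has to be checked.

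**Cost:** the wording changes cost almost nothing. Figures by setting will have wider intervals than the pooled one. Weighting widens intervals further. With an assumed design effect of 1.2 to 1.5, the half-width 1.96 × √(0.25 × design effect / n) becomes:

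- about 2.8 to 3.1 points at n = 1,495 (2.5 unweighted);
- about 3.3 to 3.7 points at n = 1,068 (3.0 unweighted);
- about 3.6 to 4.0 points at the 897 completers left after 40% loss (1,495 × 0.6; 3.3 unweighted).

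Weighting does not remove differences between union members and non-members, so the limit on conclusions is needed either way.
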